- The patient must have a blood pressure reading $\geq 130-139/80-89$ mm Hg at least during 1 clinic visit during the current pregnancy; before or at time of enrollment

OR

3. Pre-gestational diabetes

- Type 1 and Type 2 diabetics are included
- Gestational diabetes mellitus diagnosed prior to 20 weeks gestational age will also be included

Exclusion Criteria

- ***Known allergy/prior adverse reaction/any medical condition where aspirin is contraindicated***
- ***Already on aspirin prior to pregnancy***
- ***Baseline renal Disease***
- ***Baseline Proteinuria identified at time of enrollment, defined as urine analysis with 3+ protein, or urine protein to creatinine ratio ≥ 0.3***
- ***Seizure disorder on medications***
- ***Known major fetal anomalies***
- ***Multifetal gestation***

Recruitment

Patients will be recruited from the following locations:

- Texas Medical center Ross Clinic in the UT Professional Building (Suite 350)
- Texas Medical center High Risk OB Clinic in the UT Professional Building (Suite 350)
- UT Obstetrics office at Bellaire
- Harris Health Obstetrics Clinic at LBJ Hospital

Randomization

Randomization will be achieved by computer-generated random sequences, using RedCap. Permuted block randomization will be performed. Women will be randomized to 81mg/day of aspirin or 162 mg/day of aspirin.

Interventions and Procedures

Women with singleton gestations that are less than twenty weeks gestational age and meet inclusion criteria will be approached by the research staff after the study is introduced by the patient's provider. Written informed consent will be obtained from participating women at the outpatient clinic. If the patient consents, then randomization

will be performed. The results of randomization will be shared with the obstetric provider and the patient prior to starting aspirin. If the patient had already been started on 81mg/day aspirin in a prior visit then she will be informed of whether she should continue with the same dose or if she would need a higher dose based on the randomization.

[figure not shown]
After randomization, patients will then be prescribed the medication. Which will be started between 12 and 20 weeks gestational age and continued till time of delivery. The primary provider will dictate all other aspects of care.

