A medication adherence survey (Morisky medication adherence survey) will be performed to assess for compliance at 16-24 weeks of gestational age, and again at 32- 36 weeks gestational age. At the time of administration of medication adherence surveys, participants will be asked about medication side effects. ²²⁻²⁴

Blood samples (3-4 cc) and urine samples (3-4 cc) will be obtained at the time of enrollment (with the routine blood tests that are sent), to test for baseline aspirin, thromboxane and prostacyclin levels. At the time of delivery, blood samples (3-4 cc) and urine samples (3-4 cc) (with routine blood samples that are sent at time of labor admission), placental 1x1 cm specimens and cord blood will be obtained. These samples will be used for biochemical correlation with the clinical data.

The primary outcome (incidence of preeclampsia with severe features) will be determined based on clinician diagnosis, with the use of ACOG diagnostic criteria. Secondary outcomes will be determined by following the mother and the neonate clinically until the time of discharge. Patients will not be contacted after discharge from the hospital.

Figure 1. Flow Diagram

Sample Size and Feasibility

An intent-to-treat principle will be applied to all analysis. To calculate Bayesian statistical power we assumed a baseline incidence of preeclampsia in our population to be 20%. We investigated effects sizes of 50%, 40%, and 30% reduction (corresponding relative risk [RR] of 0.5, 0.6, and 0.7). We also varied the level of certainty (probability threshold for declaring benefit) from 70% to 85%. For all scenarios, we assumed a neutral prior centered at RR of 1.0 with 95% credible interval of 0.33-3.0 (excludes implausible large treatment effects). Tables 5 and 6 present the power for two total sample sizes. We will use the number of patients required to detect a 40% reduction in incidence of preeclampsia with 75% certainty and power $(1 - \beta) = 0.80$ is **220** (110 patients in each arm).

Table 5: Bayesian power for sample size N=290 using different levels of certainty

Assumed RR	Level of Certainty			
	70%	75%	80%	85%
0.50	0.97	0.95	0.93	0.89
0.60	0.91	0.88	0.83	0.76
0.70	0.80	0.75	0.68	0.59

Table 6: Bayesian power for sample size N=220 using different levels of certainty

Assumed RR	Level of Certainty			
	70%	75%	80%	85%
0.50	0.93	0.9	0.86	0.81
0.60	0.84	0.80	0.74	0.67
0.70	0.71	0.66	0.59	0.5

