In the week of November 5-9 2018, 10 patients that attended the UT Women's clinic and UT Bellaire Clinic, met inclusion criteria. Assuming a 50% enrollment rate, the study would take 12.5 months.

Statistical Tests

Selected baseline characteristics and outcome measures will be collected for each group. Descriptive statistics will be used to summarize all variables. An intent-to-treat analysis will be conducted. The rate of the primary outcome, preeclampsia, will be compared between the intervention and control group using a log binomial (or Poisson in case of nonconvergence) model to estimate relative risk and 95% confidence interval (CI). Each secondary outcome will be similarly analyzed using the best fitting generalized linear model with intervention group as the covariate. For all outcomes, we will report relative risks or differences and 95% CIs.

We will also conduct a Bayesian analysis of the primary outcome to calculate probability of treatment benefit or harm. We will use a neutral prior distribution for the intervention effect that excludes implausible large treatment effects: Normal(0, SD=0.57) in the log RR scale (prior 95% interval for the RR of 0.33-3)²⁵. We will report posterior median and 95% credible interval and probability of treatment benefit.

Subgroup Analysis. To investigate treatment effect modifier for the primary outcome, we will use a Bayesian hierarchical model with terms of interaction between treatment group (162 mg, 81 mg) and the prespecified potential moderator of BMI (30-40; >40). The conservative Bayesian approach of Dixon and Simon²⁶ allows us to specify a priori how likely (or unlikely) it is for subgroup differences to be present and to shrink the subgroup estimates to the overall mean treatment effect. A neutral prior will be used for the interaction term. Point estimates of treatment effect and 95% credible intervals will be reported along with probability of treatment benefit/harm.

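### Does the primary analysis need to adjust for the risk factors on which women enter the trial?

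*Combined protocol and SAP*

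**What the plan says.** All references are to section 2 of the combined protocol and SAP.

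- **Statistical Tests, primary outcome:** "The rate of the primary outcome, preeclampsia, will be compared between the intervention and control group using a log binomial" model, or Poisson if that fails to converge. No baseline covariate is listed.
- **Statistical Tests, secondary outcomes:** "Each secondary outcome will be similarly analyzed using the best fitting generalized linear model with intervention group as the covariate". The word *similarly* points back to the primary model, so the natural reading is that treatment is the only term there too.
- **Statistical Tests, Bayesian analysis:** "We will use a neutral prior distribution for the intervention effect", namely Normal(0, SD 0.57) on the log relative risk. No other coefficient is given a prior.
- **Randomization:** "Permuted block randomization will be performed". No stratification factor is named.
- **Inclusion Criteria:** BMI of at least 30 and any one of prior preeclampsia, at least stage I hypertension, or pre-gestational diabetes.
- **Subgroup Analysis:** BMI is the only baseline factor modelled, and only as a possible effect modifier.

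**The concern.** The three entry routes are plausible predictors of preeclampsia, yet neither the allocation nor the model uses them. In a trial of 220, one arm can by chance receive noticeably more women with prior preeclampsia. If that history is prognostic, the unadjusted relative risk in that trial moves in the direction of the imbalance. The sample size uses a posterior probability of only 75% as the threshold for declaring benefit, so a modest shift could change the conclusion. The trial is also open-label, and covariates chosen after baseline data had been seen would be open to criticism. On this view, prespecified adjustment would be cheap protection.

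**Working it through.** **1. The plan's own figure.** Inputs from Sample Size and Feasibility: control risk 0.20, RR 0.60 (so 0.12 on 162 mg), 110 per arm, threshold 0.75, prior SD 0.57 (variance s² = 0.3249).

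- Variance of the log RR: v = 0.80/22 + 0.88/13.2 = 0.0364 + 0.0667 = 0.1030.
- Posterior SD: √[v·s²/(v + s²)] = √(0.0335/0.4279) = 0.280.
- Benefit is declared if the observed log RR is below −c, where c = 0.674 × 0.280 × (0.4279/0.3249) = 0.248.
- Power: Φ[(0.511 − 0.248)/0.321] = Φ(0.82) = 0.793.

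Exact enumeration over the two binomials gives 0.796, against the stated 0.80. With RR = 1, the chance of declaring benefit is 0.224. The tabulated power is therefore that of a model without covariates.

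**2. How often imbalance occurs.** The documents give no prevalences. Assume 35/55/30% for prior preeclampsia, hypertension and diabetes, and keep women with at least one; this gives about 44/69/38%. For a factor at 44%, the SD of the difference between arms is √(2 × 0.44 × 0.56/110) = 0.067. A gap of at least 10 points (11 women) then occurs in about 15% of trials.

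**3. What adjustment buys overall.** Simulation, 20,000 trials per row, 20% vs 12%, robust Poisson combined with the planned prior; the adjusted model adds the three factors and BMI. Assumed odds ratios (prior preeclampsia, hypertension, diabetes; BMI per SD): none 1, 1, 1; 1. Weak 1.5, 1.5, 1.5; 1.2. Middle 2.5, 2, 2; 1.3. Strong 4, 2.5, 2.5; 1.5.

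| Prognosis | Variance ratio, unadjusted/adjusted | Power, unadjusted | Power, adjusted | Adjusted power at the unadjusted false-positive rate | False positives, unadjusted | False positives, adjusted |
|---|---|---|---|---|---|---|
| None | 0.980 | 0.797 | 0.804 | 0.802 | 0.225 | 0.229 |
| Weak | 0.995 | 0.795 | 0.804 | 0.798 | 0.225 | 0.231 |
| Middle | 1.018 | 0.798 | 0.816 | 0.809 | 0.224 | 0.230 |
| Strong | 1.046 | 0.798 | 0.821 | 0.815 | 0.229 | 0.235 |

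At an equal false-positive rate the power gain is 0.5, 0.3, 1.1 and 1.7 points. Even under strong prognosis the standard error falls only by a factor of √1.046 = 1.02. At an assumed 10% vs 6%, the variance ratio is 0.980 to 1.020 and power is 0.58 to 0.59 either way.

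**4. What happens in the imbalanced trials.** Null trials at 20% risk with a gap of 10 points or more in prior preeclampsia (about 7 to 8% of trials in each direction), unadjusted analysis:

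| Prognosis | Typical RR, gap favours 162 mg | False positives | Typical RR, gap favours 81 mg | False positives | Mean of the two rates |
|---|---|---|---|---|---|
| None | 1.00 | 0.22 | 0.99 | 0.24 | 0.23 |
| Weak | 0.97 | 0.25 | 1.02 | 0.20 | 0.225 |
| Middle | 0.94 | 0.30 | 1.07 | 0.16 | 0.23 |
| Strong | 0.89 | 0.37 | 1.11 | 0.12 | 0.245 |

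Adjusted, the rate stays at 0.23 to 0.24. The two directions nearly cancel, so the rate over all trials remains 0.22 to 0.23. The middle shift, ln 0.94 = −0.06, compares with a null standard error of √(2 × 0.80/22) = 0.27, or about a quarter of a standard error.

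**5. What adjustment costs.** Expected events are 22 + 13.2 = 35.2, so five non-intercept coefficients have 7 events each. At 10% vs 6% there are 17.6 events, or 3.5 each. The adjusted log-binomial failed to converge in 5 to 50% of simulated data sets, whereas the treatment-only RR is simply the ratio of two proportions. A switch to prior preeclampsia alone when events fall below 25 would trigger in 95% of trials at 10% vs 6%, and there the variance ratio is 0.997 to 1.014. It can also do harm. In null trials with an imbalance in hypertension and strong prognosis, it moved the mean log RR from −0.049 to −0.074 at 20% risk and from −0.097 to −0.129 at 10%. The entry rule makes the factors negatively related among enrolled women, so correcting one can undo an offsetting balance in another.

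**The case for a change.** The best argument for adjustment concerns the one trial that will be run, not average power. At least one of the three factors is out of balance by 10 points in about 35% of trials under the assumptions above. If prior preeclampsia is strongly prognostic and the gap favours 162 mg, the chance of a false declaration is 0.37 unadjusted against 0.24 adjusted. Fixing the covariates in advance would also close off a later choice in an open-label study.

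The conditional argument is sound in principle, and adjustment would be a legitimate design choice. It does not show a defect, for three reasons.

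- The 0.37 needs the strongest assumed prognosis and a selected 7 to 8% of trials. The background section's Table 2 places prior preeclampsia, diabetes and chronic hypertension in the same high-risk tier, so the documents give no size for the contrast among enrolled women.
- The analysis is already fixed on its natural reading. A sentence confirming treatment as the only term would remove any doubt, but that is a matter of detail.
- The protection depends on complete and accurate covariates. The plan says only "Selected baseline characteristics and outcome measures will be collected for each group", eligibility needs just one criterion, and prior preeclampsia may rest on patient history when records are unavailable.

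Evidence on the adjusted standard error is mixed. One simulation gave 95% interval coverage of 0.949 to 0.955. Another, with a relative risk of 2.5 per factor, found a typical robust standard error of 0.308 against an empirical 0.331, and null rejection of 0.060 against 0.043 unadjusted.

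One related matter is separate. The plan states "we assumed a baseline incidence of preeclampsia in our population to be 20" percent, yet elsewhere says "The primary outcome (incidence of preeclampsia with severe features) will be determined based on clinician diagnosis". That mismatch bears on what the power figure means, and adjustment would not resolve it.

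**Conclusion.** The concern does not hold. The treatment-only analysis is valid under randomization, agrees with the unstratified allocation described, and carries the power the plan claims (0.796 against 0.80). The benefit of adjustment rests wholly on assumed prevalences and prognostic strengths. Across those assumptions it runs from a 2% loss of precision to a variance ratio of about 1.05, and is worth 0 to 2 power points at an equal false-positive rate. A separate simulation gave variance ratios of 0.98 to 1.08 at 20% control risk and 0.98 to 1.03 at 10%, with power up by 0 to 2.5 points. Set against a five-coefficient model on about 35 events, perhaps 18, and a fallback that can move the estimate the wrong way, this is a debatable trade-off. The plan needs no change on this point.

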Evidence suggests that in preeclamptic patients there is an imbalance in the prostacyclin /thromboxane balance favoring thromboxane. Thromboxane is a vasoconstrictor while prostacyclin is a vasodilator.⁹ The pathophysiology of action of aspirin for preeclampsia prophylaxis is believed to be due to its preferential inhibition of COX-1 at low doses (60-150mg/day)¹⁰.

The American College of Obstetrics and Gynecology in July 2018, published a committee opinion supporting the USPSTF guideline criteria for the use of low dose aspirin for preeclampsia prophylaxis. The recommended dose is 81mg/day of aspirin, and it is to be used in women at high risk for preeclampsia. Women were considered to be at high risk if they had at least a 8% incidence of preeclampsia (table 2). The initiation of aspirin was to be done at 12-28 weeks gestation, optimally prior to 16 weeks gestational age.¹⁰

Table 2: ACOG recommendations for low dose aspirin (LDA) use for preeclampsia prophylaxis

Risk Level	Risk Factors	Recommendations
High	History of preeclampsia Type 1 or 2 Diabetes Chronic Hypertension Multifetal Gestation Renal Disease	LDA if \geq 1 Risk Factor

	Autoimmune Disease (SLE, APLS)	
Medium	BMI \geq 30	LDA if > 1 Risk Factor
	Nulliparity	
	Fam. Hx of preE (mother or sister)	
	Sociodemographic characteristics (AAF, low SES)	
	Age \geq 35	
	Personal Hx factors (hx of SGA , prior adverse pregnancy outcomes)	

As illustrated in table 3 there have been multiple randomized controlled trials that support the use of higher aspirin doses for preeclampsia prophylaxis. A recent systematic review and metaanalysis of randomized controlled trials, evaluating a total of 14,668 patients noted that the incidence of preeclampsia depended on the gestational age at initiation of aspirin and the dosing of aspirin used. With a clinically significant decrease in rate of preterm preeclampsia noted when the aspirin dose is ≥ 100 mg/day and when it is initiated at ≤ 16 weeks (table 4)¹¹.

Table 3: Randomized Trials with higher dose Aspirin for prevention of Preeclampsia

Study Location Year	Gestation al Age at enrollment	N	Comparison	Preeclamps ia Outcomes
Rolnik Multicenter Europe 2017¹²	11-14 weeks	1776	150mg ASA vs placebo	Preterm preeclampsia 4.3% in placebo group vs 1.6% in ASA

				group (p=0.0004)
Yu Multicenter International 2003¹³	22-24 weeks	844	150mg ASA vs placebo	19% in placebo group vs 19% in ASA group (p=0.6)

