Sureau Multicenter France 1991¹⁴	15-18 weeks	229	150mg ASA vs 150mg ASA + dipyrimadole 225 mg/day vs placebo	No difference between groups.

Table 4: Metaanalysis with Relative Risk of preterm Preeclampsia detailed by onset of treatment and dose of aspirin

Dose	Trials Participants	Gestational Age	RR (95% CI)	P-value
< 100 mg	10 trials 11,855 pts	≤ 16 weeks	0.59 (0.29- 1.19)	0.14
		> 16 weeks	1.00 (0.80- 1.25)	0.99
≥ 100 mg	7 trials 2,813 pts	≤ 16 weeks	0.33 (0.19- 0.57)	0.001
		> 16 weeks	0.88 (0.54- 1.43)	0.60

Aspirin resistance is a phenomenon that refers to the inability of aspirin to reduce the production of thromboxane A2. It is detected by laboratory tests that either measure directly the thromboxane A2 levels, or indirectly the platelet function that depends on platelet thromboxane production.¹⁵ A recent study evaluated aspirin resistance in pregnant patients, and noted that aspirin resistance was decreased as the dosing of aspirin increased. With a incidence of 30% , 10% and 5% of aspirin resistance at doses

of 81, 121 and 162mg respectively.¹⁶ Moreover, data has emerged in other fields linking obesity, female gender, and poor glycemic control to aspirin resistance.¹⁷

At baseline, obesity is linked to a low grade inflammation state causing lipid peroxidation and in turn a persistent platelet activation, causing higher levels of thromboxane to be present in this population.¹⁸ Also, obesity is a established risk factor for preeclampsia.² In a population-based cohort study including 503,179 nulliparous patients, obese patients had a fourfold increase in incidence of preeclampsia in comparison to those with a normal BMI.¹⁹

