2. RESEARCH DESIGN AND METHODS

Objective

To compare the incidence of preeclampsia with severe features in the 81mg/day aspirin group to the 162mg/day aspirin group. Maternal and neonatal outcomes will also be compared between the two groups.

Population

Obese pregnant women with a singleton gestation at less than 20 weeks and either a history of preeclampsia in a prior pregnancy or stage I hypertension or pre-gestational diabetes.

Obese is defined as a BMI greater than 30 at time of the first prenatal visit.

Intervention

Aspirin at a dose of 162mg/day (ie two 81mg/day pills daily) to be started as early as 12 weeks gestational age till time of delivery

Control

Women who receive the standard recommended 81 mg/day dosing of aspirin from as early as 12 weeks gestational age till time of delivery

Outcome (Primary)

Incidence of preeclampsia

Preeclampsia with severe features diagnosis will be abstracted from the medical charts. This will be used for the primary outcome. The diagnosis will then be adjudicated by three maternal fetal medicine specialists, to assess for compliance with ACOG established criteria.² The adjudicated diagnosis will be used for the measurement of the secondary outcome.

Other Secondary Outcomes

- Maternal Outcomes
 - o Incidence of preterm preeclampsia
 - o Gestational Hypertension
 - o Abruptio
 - o Eclampsia
 - o HELLP syndrome
 - o Postpartum Hemorrhage
 - o Other maternal bleeding (?)
 - o Need for blood transfusion
- Neonatal Outcomes
 - o Gestational age at delivery
 - o Delivery at < 37 weeks
 - o Apgar score at 5 min ≤ 5
 - o Small for gestational age
 - o NICU length of stay
 - o Intraventricular Hemorrhage Grade III-IV
 - o Bronchopulmonary Dysplasia
 - o Necrotizing Enterocolitis

Study Design

Randomized controlled open-label comparative effectiveness trial.

Inclusion Criteria

- A singleton gestation at less than 20 weeks at time of enrollment, with a BMI greater than or equal to 30 and one of the following:

1. History of preeclampsia in a prior pregnancy

-Diagnosis will be obtained by review of records, and if unavailable then patient history. Preeclampsia diagnosis may be made in antepartum or postpartum period.

OR

2. At least stage I hypertension during pregnancy

-Stage I hypertension is defined as a systolic blood pressure between 130-139 mm Hg or diastolic blood pressure between 80-89 mm Hg²¹

- This blood pressure criteria is met regardless of medication usage

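### Should gestational age at randomisation be a second prespecified moderator, given that the background links aspirin's benefit to starting by 16 weeks?

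*Combined protocol and SAP*

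**What the plan says.** Two parts of the protocol bear on timing.

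- **Background and Significance.** The cited guidance puts the start of aspirin at 12 to 28 weeks, "optimally prior to 16 weeks gestational age". The cited meta-analysis found its reduction in preterm preeclampsia "when the aspirin dose is ≥ 100 mg/day and when it is initiated at ≤ 16 weeks". Table 4, "Metaanalysis with Relative Risk of preterm Preeclampsia detailed by onset of treatment and dose of aspirin", gives RR "0.33 (0.19- 0.57") for at least 100 mg started by 16 weeks, and 0.88 (0.54 to 1.43) for later starts. Below 100 mg the figures are 0.59 (0.29 to 1.19) and 1.00 (0.80 to 1.25).
- **Research Design and Methods.** Eligibility requires "A singleton gestation at less than 20 weeks at time of enrollment". On the medication, the text reads "Which will be started between 12 and 20 weeks gestational age and continued till time of delivery". Women may already be taking the lower dose: "If the patient had already been started on 81mg/day aspirin in a prior visit", they are told at randomisation whether to continue or change.

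Randomisation uses permuted blocks, and no stratification factor is named. Under Statistical Tests, the primary model has treatment group as its only term. The one planned effect modifier is "the prespecified potential moderator of BMI (30-40; >40", fitted in a Bayesian hierarchical model that shrinks subgroup estimates toward the overall effect. No analysis by gestational age at enrolment, randomisation or start is described.

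**The concern.** The protocol supports a higher dose with a table split by both dose and timing, enrols on both sides of that table's 16-week cut, and then plans no analysis by timing. If late starters gain little from the higher dose, the overall relative risk is pulled toward 1 and power falls. After a null result, readers could not tell an ineffective dose from a diluted effect, and any later look at timing would be post hoc. The raw early-versus-late contrast in Table 4 at 100 mg or more is strong (p = 0.009), so the omission looks like an oversight.

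**Working it through.** **1. The plan's own figure.** Inputs from Sample Size and Feasibility and Statistical Tests: control rate 20%, RR 0.6 (so 12%), 110 per arm, prior Normal(0, 0.57) on log RR, benefit declared if P(RR < 1) > 0.75.

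- SE of log RR = √[0.80/(110 × 0.20) + 0.88/(110 × 0.12)] = √(0.0364 + 0.0667) = 0.321.
- Weight on the data: w = 0.57²/(0.57² + 0.321²) = 0.759.
- Benefit is declared when −log RR exceeds 0.6745 × 0.321/√0.759 = 0.249.
- Power ≈ Φ[(0.511 − 0.249)/0.321] = Φ(0.817) = 0.79.

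Exact enumeration of the two binomials gives 0.796, against 0.80 in Table 6.

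**2. What Table 4 says about timing.** SE of log RR = ln(upper/lower)/3.92, which gives 0.280 and 0.248 (100 mg or more, early and late) and 0.360 and 0.114 (below 100 mg, early and late).

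| Early-to-late ratio of RRs | Estimate | 95% CI | p |
|---|---|---|---|
| 100 mg or more: 0.33/0.88 | 0.375 | 0.18 to 0.78 | 0.009 |
| Below 100 mg: 0.59/1.00 | 0.59 | 0.28 to 1.24 | 0.16 |
| Higher versus lower dose: 0.375/0.59 | 0.64 | 0.22 to 1.80 | 0.39 |

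Only the last row bears on 162 mg versus 81 mg. Its SE is √(0.280² + 0.248² + 0.360² + 0.114²) = 0.532, and ln 0.636 = −0.453. Both dose bands lean toward early starts, so timing may act on both arms alike and largely cancel in the dose contrast. Table 4 also concerns preterm preeclampsia, whereas the Objective here is preeclampsia with severe features.

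**3. What dilution would cost.** Take the indirect point values as true: 0.33/0.59 = 0.559 early and 0.88/1.00 = 0.88 late. Their intervals are 0.23 to 1.37 and 0.52 to 1.50. The late share s is not in the documents, so a range is assumed. Pooled RR = (1 − s) × 0.559 + s × 0.88.

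| Late share (assumed) | Pooled RR | Power at 110 per arm |
|---|---|---|
| 25% | 0.64 | 0.74 |
| 50% | 0.72 | 0.62 |
| 75% | 0.80 | 0.50 |

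A moderator term would restore none of this power. Table 6 already shows the consequence of a weaker effect: 0.66 at RR 0.7, which here corresponds to s = (0.70 − 0.559)/(0.88 − 0.559) = 0.44.

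**4. What the extra term could show.** The interaction SE combines the two strata. For an even split (55 per arm in each), the variance of log RR is 0.217 early and 0.158 late, so SE = √0.375 = 0.612. With 25% and 75% late starts it is 0.679 and 0.734. For a true ratio of 0.636:

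| Late share (assumed) | SE | Power (two-sided 5%) | Chance of estimate above 1: Φ(−0.453/SE) |
|---|---|---|---|
| 25% | 0.679 | 0.10 | 0.25 |
| 50% | 0.612 | 0.11 | 0.23 |
| 75% | 0.734 | 0.09 | 0.27 |

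With an even split, an estimate of 0.64 would carry an interval of about 0.19 to 2.11. With 25% late, the late stratum expects 27.5 × (0.20 + 0.176) = 10 events in both arms together.

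**5. Which variable.** Table 4 is split by onset of aspirin. A woman who began 81 mg at 12 weeks and was randomised at 18 would be early by that definition but late by gestational age at randomisation. The baseline variable that suits an intention-to-treat analysis is therefore not the one the background evidence describes.

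**6. Validity of the primary analysis.** Randomisation balances gestational age between arms in expectation. The relative risk is collapsible, so leaving gestational age out of the model does not bias the average effect over the women enrolled.

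**The case for a change.** The best argument for adding the term is that it is nearly free and is credible only if set down before outcomes are compared by arm. Gestational age at enrolment is needed for eligibility, the hierarchical model is already planned and suits imprecise subgroups, and counts by stratum and arm would show readers how much of the trial lies in the setting where Table 4 shows benefit. An exploratory label would meet the power problem.

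The description of the plan is right: BMI is the only moderator, and the start window crosses 16 weeks. Reporting gestational age at randomisation by arm would be a reasonable courtesy, and the plan already promises descriptive summaries of selected baseline characteristics. Low cost, however, does not make the omission a fault. The primary analysis and sample size would not change, and an estimate this imprecise, shrunk further toward the overall effect, would leave a null result as ambiguous as before. An adjusted model with gestational age as a covariate would still estimate an average effect and would not address moderation.

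Table 3 adds little. Its 11 to 14 week trial reports preterm preeclampsia, while its 22 to 24 week trial gives 19% versus 19% without that restriction and lies outside this trial's window. Its 15 to 18 week trial straddles the 16-week cut.

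**Conclusion.** The concern does not hold. As written, the plan gives a sound answer to its own question, the average effect of 162 mg against 81 mg in obese women enrolled before 20 weeks. The background argues from body weight and aspirin response, so BMI as the single moderator follows from the hypothesis. The striking timing contrast (0.375, p = 0.009) belongs to aspirin against placebo; for the dose comparison under test the evidence is 0.64 with an interval of 0.22 to 1.80. A timing term would have power of about 0.09 to 0.11 and would change no conclusion of the trial.

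These sizes assume a 20% control rate, 110 women per arm, the indirect point values from Table 4, and a late-start share of 25% to 75%, which the documents do not give. The interaction is weakly estimated across that whole range, so the conclusion does not depend on where the share falls.
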